2.4 Timelines

Planned milestones are as follows:

First subject in: December 2020
Interim analysis: After 15th subject complete* (est. May 2021)
Last subject complete: est. 30 September 2021
Full database delivered to SSU: (est. 30 October 2021)
Blind data review: SSU create tables: 6-8 weeks
Team review blind outputs
Data Base lock
Statistical analysis: 6-8 weeks after database lock
Statistical report: containing TFLs and brief text

*Interim analysis to take place once 15 participants have had their final assessment at day 57.

Final analysis will take place once all participants have had their final assessment at day 57 or have discontinued and the data has been fully cleaned and the database locked.

Completion of the SAP, data cleaning and a blind review will take place prior to data base lock. During blind review all decisions about protocol deviations (ITT and PP populations) and analyses (such as assumptions checking) will be made. Once all these activities have taken place then the database will be locked and unblinded.

3. Data Collection:

Data is to be collected in a custom electronic data capture system designed by the Clinical Trials Research Unit (CTRU) within the University of Sheffield. Adverse events will be coded to MedDRA preferred terms & system organ class within the database. Data will be provided to the SSU as clean csv files.

Data transfers between the study team and Pfizer will be in csv format, final data transfers (after final analysis) from the SSU to Pfizer will be in pre-agreed SAS format. For further details of the transfer of documentation, data and reporting between the study team, the SSU and Pfizer see section 8.

4. Analysis Objectives:

4.1 Primary objective:

To determine whether twice daily treatment with crisaborole (2%) ointment, compared to betamethasone valerate (0.1%) cream, for up to 4 weeks is a cause of skin atrophy in patients with atopic dermatitis.

4.2 Secondary objective:

To determine whether there is a difference between crisaborole (2%) ointment and betamethasone valerate (0.1%) cream on:

- Kinetics of changes in epidermal thickness
- Tolerability
- Skin barrier function
- Skin dryness
- Levels of natural moisturising factor

4.3 Exploratory objectives:

To investigate whether OCT-derived biomarkers (other than the established structural OCT biomarker) enable the accurate quantification of tissue changes (vascular and matrix) associated with epidermal atrophy in response to TCS treatment. Biomarker measurements from the images will include:

- Superficial plexus depth (μm) from angiographic OCT images
- Mean vessel diameter (μm) from angiographic OCT images
- Vessel density (segments/ mm^2) from angiographic OCT images
- Collagen matrix index from polarisation sensitive OCT images

To investigate whether FTIR spectroscopy-derived biomarkers enable the accurate quantification of skin barrier condition and function in response to TCS treatment. Biomarker measurements from the spectra will include:

- NMF levels in the skin
- Lipid Structure

To investigate the number of participants with FLG loss-of-function mutations and explore if there is any evidence of a relationship to treatment effects.

To identify (by completing the objectives above) a panel of biomarkers that best characterises epidermal atrophy.

5. Analysis Sets and Protocol Deviations

Full Analysis Set (FAS): All subjects who were randomised into the study.

Per-protocol set (PPS): All participants who are deemed to have no major protocol violations that could interfere with the objectives of this study. This is a sub-population of the FAS.

Safety set: All randomised participants who receive at least 1 dose of test or reference cream.

All efficacy analyses and summaries will be performed on the FAS. If there are concerns about protocol deviations at the blind review, then a sensitivity analysis of the primary objective may be performed on the PPS.

Safety summaries will be performed on the safety set.

Prior to unblinding, a blind review of the data will be performed. The objective of the review is to identify protocol deviations and data queries and to make decisions regarding data analytical issues under blind conditions. Important violations of eligibility criteria and other deviations from the protocol will be assessed in cooperation with the study team. Important deviations from the protocol may lead to exclusion of a participant from the PPS. All deviations will be discussed and agreed prior to the unblinding of the data.

6. Endpoints and Covariates

6.1 Primary endpoints

- Change in Epidermal thickness measured by structural OCT (day 29 - day 1)

6.2 Secondary endpoints

- Epidermal thickness measured by structural OCT during and after 28 days treatment:
 - Change in epidermal thickness (day 15 - day 1)
 - Change in epidermal thickness (day 57 - day 29)
- Erythema (visual redness) score during and after 28 days treatment:
 - Erythema score change from baseline (day 15, day 29, day 57)
- Objective redness as assessed with a Mexameter during and after 28 days treatment
 - Objective redness change from baseline (day 15, day 29 and day 57)
- Trans-Epidermal Water Loss during and after 28 days treatment
 - TEWL change from baseline (day 15, day 29, day 57)
- Skin barrier integrity after 28 days treatment:
 - Difference in TEWL_{ts20} between the two treatments (day 29)
- Visual skin dryness during and after 28 days treatment:
 - Dryness change from baseline (day 15, day 29, day 57)
- NMF at the end of treatment (quantified from superficial stratum corneum samples):
 - Difference between the two treatments (day 29)

6.3 Exploratory endpoints: **Angiographic OCT endpoints**

- Superficial plexus depth (µm)
 - Change from baseline/day 1 in superficial plexus measurement (day 15, day 29, day 57)
- Mean blood vessel diameter (µm)
 - Change from baseline/day 1 in mean blood vessel diameter (day 15, day 29, day 57)
- Blood vessel density(segments/mm²)
 - Change from baseline/day 1 in blood vessel density (day 15, day 29, day 57)

Polarisation sensitive OCT image (PS OCT) endpoints

- Collagen matrix index
 - Change from baseline/day 1 in collagen matrix index (day 29)

FTIR spectroscopy endpoints

- Carboxylate levels
 - Change from baseline/day 1 in carboxylate levels (day 15, day 29, day 57)
- Stratum corneum lipid structure (FTIR and tape stripping)
 - Difference between groups in stratum corneum lipid structure (day 29)
- Number if FLG loss-of-function mutation carriers
 - Count result from saliva sample (day 1)
- Descriptive statistics split by FLG mutation grouping of TEWL split by mutation grouping (day 1, day 15, day 29, day 57)
 - TEWL (day 1, day 15, day 29, day 57)
 - Epidermal thickness (day 1, day 15, day 29, day 57)

Visual scoring of the dryness of the subject's skin by an expert will take place at baseline (day 1), after 2 weeks treatment (day 15), after 4 weeks treatment (day 29) and 4 weeks after treatment cessation (day 57). Scores will be on a scale from 0 to 4 and will be graded by two observers independently. The upper and lower volar forearms on each side will be combined to give one overall result for the right and one overall result for the left.

NMF levels

Samples for analysis of stratum corneum NMF levels will be collected by tape stripping after 4 weeks of treatment (single time point, day 29). One sample will be collected from each sampling site (tape-strips/discs 1-3 on lower right and left volar forearm). The samples will be analysed separately.

Product Consumption

Product consumption will be based on the difference in weight of the ointment and cream between the start (day 1) and end (day 29) of treatment phase.

Adverse Events

Participants will record AEs throughout the study in their diaries with the information transferred to the CRF at day 29 and day 57.

FLG loss-of-function mutations

Saliva samples will be collected at baseline (day 1) to obtain genomic DNA for determination of participant FLG gene status. Samples will undergo DNA extraction and genotyping at the

University of Sheffield for the 5 common European loss-of-function FLG mutations that have been reported to confer increased AD risk.

7. Statistical Analyses

The primary and secondary analyses will identify where there is evidence of a difference between the two treatments in the change from baseline and which biomarkers are able to identify this difference in the clinical trial setting. Exploratory analyses will investigate whether a subset of the OCT endpoints can be used to non-invasively identify skin changes.

Outcome and demographic data will be summarised at each time point using appropriate descriptive statistics such as N, mean, standard deviation, minimum, lower quartile, median, upper quartile and maximum.

7.1 Primary Analysis

The primary analysis of change in epidermal thickness over 28 days treatment will be estimated using a repeated measures mixed model with change from day 1 as the outcome, treatment, timepoint as factors together with a treatment by timepoint interaction, subject as a random effect and baseline as a covariate. The estimate of change from baseline to day 29 from this model will be the primary outcome, the estimate of change from day 1 to day 15 and change from day 29 to 57 will be secondary as described by in section 7.2.

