7.2 Secondary Analysis

The analysis of three of the secondary endpoints will use a repeated measures mixed model with change from day 1 (to day 15, day 29, day 57) as the outcome, treatment, timepoint as factors together with a treatment by timepoint interaction, subject as a random effect and baseline as a covariate.

The model will be used to estimate the difference between treatment arms for the change from baseline to day 29.

If there is a significant difference observed in the change from baseline to day 29, then the change from day 1 to day 15, and the change from day 29 to day 57 will also be assessed. If there is no statistically significant difference in the change from baseline to day 29 then we will not test further timepoints.

Summary statistics will be presented for all timepoints.

This applies to:

- Change in epidermal thickness (change from day 1 to day 15, and from day 29 to day 57 as secondary endpoints)
- Change in redness/erythema
- Change in Trans-Epidermal Water Loss (TEWL)
- Change in visual skin dryness

The Change in TEWL_{ts20} after 28 days treatment will use an ANCOVA model with change from day 1 to day 29 as outcome, treatment as a factor, subject as a random effect and baseline as a covariate. The analysis of Natural Moisturising Factor after 28 days treatment (day 29) will

use a paired analysis (such as a t-test, depending on the distribution of the data) unless it is necessary to adjust for any covariates, in which case an ANCOVA will be used. If any of the above models do not fit satisfactorily or appear to be over fitted the analysis may be changed to look at change from baseline to day 29 and change from day 29 to 57 separately.

Since these analyses are exploratory, no adjustment for multiplicity will be made.

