14.2.15 Total Product consumption (Safety Analysis Set)
14.3.1 Number of patients experiencing AEs (Safety Analysis Set)
14.3.2 Adverse Events by system organ class and preferred term (Safety Analysis Set)
14.3.x Adverse Events - further tables as appropriate (Safety Analysis Set)
BDR1.1 Summary of epidermal thickness by location (Full Analysis Set)
BDR1.2 Summary of epidermal thickness change by location (day 29 – day 1) (Full Analysis Set)
BDR1.3 Summary of epidermal thickness change after treatment cessation by location (day 57 – day 29) (Full Analysis Set)
BDR2.1 Summary of TEWL (g/m²h) by location (Full Analysis Set)
BDR2.2 Summary of TEWL (g/m²h) change by location (day 15 – day 1, day 29 – day 1, day 57 – day 1) (Full Analysis Set)
BDR3.1 Summary of TEWL_{ts20} (g/m²h) by location (Full Analysis Set)
BDR3.2 Summary of TEWL_{ts20} (g/m²h) change by location (day 29 – day 1)
BDR4.1 Summary of NMF by location (Full Analysis Set)
BDR4.2 Summary of NMF change by location (day 15 – day 1, day 29 – day 1, day 57 – day 1) (Full Analysis Set)
BDR5.1 Summary of visual scores for redness (erythema) by location (Full Analysis Set)
BDR5.2 Summary of visual scores for redness (erythema) change by location (day 15 – day 1, day 29 – day 1, day 57 – day 1) (Full Analysis Set)
BDR6.1 Summary of Objective redness (Mexameter) by location (Full Analysis Set)
BDR6.2 Summary of Objective redness (Mexameter) change by location (day 15 – day 1, day 29 – day 1, day 57 – day 1) (Full Analysis Set)
BDR7.1 Summary of Dryness by location (Full Analysis Set)
BDR7.2 Summary of Dryness change by location (day 15 – day 1, day 29 – day 1, day 57 – day 1) (Full Analysis Set)
BDR8.1 Summary of Superficial plexus depth (μm) by location (Full Analysis Set)
BDR8.2 Summary of Superficial plexus depth (μm) change by location (day 15 – day 1, day 29 – day 1, day 57 – day 1) (Full Analysis Set)
BDR9.1 Summary of Mean blood vessel diameter (μm) by location (Full Analysis Set)

BDR9.2	Summary of Mean blood vessel diameter (μm) change by location (day 15 – day 1, day 29 – day 1, day 57 – day 1) (Full Analysis Set)
BDR10.1	Summary of blood vessel density (segments/ m^2) by location (Full Analysis Set)
BDR10.2	Summary of blood vessel density (segments/ m^2) change by location (day 15 – day 1, day 29 – day 1, day 57 – day 1) (Full Analysis Set)
BDR11.1	Summary of collagen matrix index by location (Full Analysis Set)

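### SAP 7.1 leaves the covariance of the primary mixed model unstated; read literally, the day-29 SE, confidence interval and p-value are right only in special cases

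*SAP*

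**What the plan says.** Protocol 10.4.2 analyses the primary endpoint with a paired analysis: a mean difference between forearms with a 95% confidence interval, and a non-parametric alternative if the distribution calls for it.

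SAP 7.1 instead fits a repeated measures mixed model to change from day 1, with "treatment, timepoint as factors together with a treatment by timepoint interaction, subject as a random effect and baseline as a covariate". The day-29 estimate is primary, and "the estimate of change from day 1 to day 15 and change from day 29 to 57 will be secondary". The SAP gives no residual covariance, no forearm-level or visit-level random term and no degrees-of-freedom method.

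SAP 7.2 carries the model over: "The analysis of three of the secondary endpoints will use a repeated measures mixed model with change from day 1". It also makes the day-29 result a gate: "If there is no statistically significant difference in the change from baseline to day 29 then we will not test further timepoints". It adds a fallback: "If any of the above models do not fit satisfactorily or appear to be over fitted the analysis may be changed", to separate analyses of the change to day 29 and the change from day 29 to 57.

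On blind review, SAP 2.4 says: "During blind review all decisions about protocol deviations (ITT and PP populations) and analyses (such as assumptions checking) will be made". SAP 5 gives one aim of that review as "to make decisions regarding data analytical issues under blind conditions". The blind-review tables for thickness in SAP 9 are of the type "Summary of epidermal thickness change by location". SAP 7.9 lists only the interim analysis as a change from the protocol.

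**The concern.** The six changes from one participant are unlikely to be equally correlated. The three changes on a forearm all subtract the same day-1 reading, which the other forearm does not share; this raises correlation within a forearm. The two forearms are also measured in the same session, so they may share a visit effect; this raises correlation between forearms at the same visit. A single subject effect cannot represent either pattern.

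The day-29 treatment difference is then tested against a residual pooled over three visits, one of them four weeks after treatment stops, and not against the spread of the within-participant day-29 differences. SAP 2.3 says that the SD of that difference is not available in the literature. A paired analysis estimates it from the trial's own data; the model, read literally, puts an unstated assumption in its place.

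With complete data the point estimate is little affected. At stake are the SE, interval and p-value of the only primary test, the gate to the other timepoints, and the day 29 to 57 contrast from the same model.

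**Working it through.** **Inputs from the documents.** SD of change 5 µm per forearm; difference 3.55 µm (Protocol Table 10.1; the text gives −4.44 against −0.88, or 3.56); 33 completers; two-sided 5% (SAP 7.5). The documents give no correlations, so every correlation below is an assumption.

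**The plan's own figure.** A two-sample t-test with difference 3.55 and SD 5 has 79.8% power at 32 per group and 81.1% at 33. With 10% dropout, 33/0.9 = 36.7, so 37. The sample size reproduces and is not in dispute.

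**Closed form** (literal model, complete data, equal variances, no baseline covariate). Let *rw* be the correlation for the same forearm at different visits, *rb* for opposite forearms at the same visit, and *rc* for opposite forearms at different visits. The 15 pairs among six values split 6, 3 and 6, so the mean correlation is m = 0.4rw + 0.2rb + 0.4rc.

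- Model variance of the day-29 difference: 2 × 25 × (1 − m)/33
- True variance: 2 × 25 × (1 − rb)/33
- Variance ratio: (1 − m)/(1 − rb), which equals 1 only if rb = (rw + rc)/2

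Examples (rw/rb/rc):

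- 0.5/0.5/0.5: model SE 0.870, true SE 0.870 µm; ratio 1.00.
- 0.7/0.3/0.2: m = 0.58 − 0.16 = 0.42; model SE 5√(1.16/33) = 0.937, true SE 5√(1.4/33) = 1.030; ratio 0.91, type I error about 7.4%.
- 0.3/0.6/0.2: m = 0.32; model SE 5√(1.36/33) = 1.015, true SE 5√(0.8/33) = 0.778; ratio 1.30, about 1.1%.

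Unequal variances matter too. With all correlations 0.3 and SDs 3/5/4 at days 15/29/57, the ratio is 0.82 (about 10.6%). With SDs 5/5/7 it is 1.16 (about 2.3%).

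**Simulation** (REML, baseline covariate, no treatment difference, n = 33, day-29 SD of change 5 µm, 5,000 replicates per scenario, Monte Carlo error about 0.3 points). Assumed scenarios: A, shared day-1 reading error only; B, one third of the change variance is a visit effect common to both forearms; C, that visit effect dominates; D, persistent forearm-specific response; E, a mixture.

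| | rw/rb/rc | closed-form SE ratio | literal model, type I | unstructured visits within forearm, type I |
|---|---|---|---|---|
| A | 0.50/0/0 | 0.894 | 7.6% | 5.3% |
| B | 0.50/0.33/0.17 | 1.00 | 3.8% | 2.8% |
| C | 0.50/0.72/0.36 | 1.35 | 0.6% | 0.7% |
| D | 0.75/0/0 | 0.837 | 9.8% | 5.2% |
| E | 0.68/0.36/0.24 | 0.935 | 7.0% | 3.5% |

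The baseline covariate shifts the results somewhat from the closed form. A repeat of the literal model gave 6.7%, 4.0%, 1.1%, 9.4% and 6.5%. The baseline-adjusted paired analysis gave 4.4% to 5.1% (4.6% to 5.8% in the repeat). The 7.2 fallback, day 29 alone with a random subject, gave 4.5% to 5.5%. More extreme assumptions widen the literal range: 16% if forearm-response variance peaks at day 29, and 0.1% if nearly all visit variation is shared. I do not rest the point on these.

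**Day 29 to 57 contrast.** With equal variances the variance ratio is (1 − m)/(1 − rw − rb + rc), giving SE ratios of 1.26, 1.41, 1.91, 1.67 and 1.67 for A to E. With correlations 0.3 and unequal SDs the direction reverses: SDs 3/5/4 give 1.20 against 1.32 µm (0.91), and 5/5/7 give 1.69 against 1.77 µm (0.95).

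**Degrees of freedom.** The literal model uses about 160. If the SE is correct but truly carries 32, using 160 gives 5.7% instead of 5.0%.

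**The case against.** The strongest reply is that *repeated measures* already signals a residual covariance over visits, so the literal reading gives those words no work to do. That is possible. An unstructured covariance within forearm brings A, D and E to 5.3%, 5.2% and 3.5%. It still does not let the forearms share a visit effect, so the test is conservative when they do (B and C). The cost to power may be small: in C the literal model's SE was 0.86 µm against a true 0.61, yet a 3.56 µm difference would be detected with about 99.9% power by normal approximation. The interval would still be too wide.

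Blind review and the 7.2 fallback could both lead to a correction. Neither requires one: the fallback is optional and has no trigger. The listed blind-review tables for thickness are summaries by location, although a table list does not define the whole review.

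Four stronger readings are tempting and not supported.

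- That the primary test is anti-conservative. Scenarios A and D, and the 16% case, set the between-forearm correlation to zero, whereas SAP 2.3 assumes it is positive. Positive-correlation cases fall on both sides.
- That the plan abandons pairing. A subject effect with both forearms in the model is still a within-participant comparison.
- That the recovery SE is always too wide. The unequal-SD cases show otherwise.
- That the permitted room range of 20±2 °C and 45±10% humidity (Protocol 7.7.1) demonstrates a shared visit effect. The range is a control measure, and the documents do not say that thickness varies with it; a shared effect is only plausible.

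**Conclusion.** The concern holds as a gap in specification that affects the primary inference. Two competent statisticians could fit different models from SAP 7.1 and report different day-29 intervals and p-values. Under the literal reading these are correct only in special cases.

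The range of about 1% to 10% for type I error illustrates what assumed covariances can do; it is not an estimate for this trial. Direction and size cannot be determined from the documents. The day 29 to 57 contrast is exposed in the same way, in either direction. The degrees-of-freedom choice is minor. The missing entry in SAP 7.9 is a documentation point. This should be fixed; confidence is medium, because the intended covariance may be better than the text shows.

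**What to change.** In SAP 7.1, define for each participant the change from day 1 on the crisaborole forearm minus the change from day 1 on the betamethasone forearm. Then choose one of:

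1. Regress the day-29 difference on the day-1 forearm difference. The intercept is the treatment effect, with a 95% confidence interval on n − 2 df (31 with 33 completers). This is the protocol's paired analysis with a baseline adjustment, and is the simplest choice.
2. Model these differences over days 15, 29 and 57 with visit, day-1 difference by visit, unstructured covariance and Kenward-Roger df. With complete data this gives the same day-29 estimate as option 1.
3. Keep the six-row model, but state a covariance that allows correlation over visits within a forearm and a visit effect common to both forearms, and name the df method.

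Use the same choice for the repeated-measures endpoints in 7.2, and list the move from the protocol's paired analysis in 7.9. The cost is SAP wording before unblinding; no new data are needed.

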7.5.1 Randomization

Allocation of the treatments to the test sites (right/left forearm) will be randomised (to avoid site position-dependent artefacts) 1:1 using a randomization schedule (list) provided by the Statistical Services Unit. The list will be numbered using the unique participant randomization number, such that participant 001 will be dispensed products according to the first anatomical site allocation on the list and so on. The Sheffield Teaching Hospitals Pharmacy will undertake and document the randomization and label the IP's with the site of application upon issue to the site research facility team. Only the Pharmacy and study Statistician (SSU) will have access to the randomisation master list.

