8.7 Treatment regimen

Every enrolled participant will undergo the same intervention, which involves the use of 2 investigational products according to a predefined regimen (Table 8.2).

Table 8.2: Treatment conditions

Treatment site	Investigational Product
Right/left forearm	Betamethasone Valerate (0.1%) cream
Right/left forearm	Crisaborole (2%) ointment

Twice-daily self-administered application of 1 finger-tip units of either crisaborole (2%) ointment or betamethasone valerate (0.1%) cream to the designated treatment areas on the volar side of the respective forearm for 28 days. The 2 daily applications should be conducted once in the morning and once in the evening, separated by at least 6 hours. When washing, the product should be applied after washing (not before). Randomized site allocation to avoid site dependent effects.

Participant diaries will be provided to record product usage (compliance) and provide usage instructions, including a visual guide to the IP allocation.

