2.2 Randomisation

Screening will take place either before or at the same visit as day 1. Those eligible to take part will be randomised on day 1 with each subject testing both treatments – one on each of the left or right lower volar forearm. The randomisation list will be provided by the SSU and the SSU will unblind the database after database lock. The interim analysis has been designed to be done on blinded data.

The pharmacy and a statistician (independent of the study statistician) will have access to the randomisation master list. Since only the research team assessing the study endpoints are blind to the treatment allocation and participants are all prescribed both treatments, no emergency unblinding arrangements are necessary.

2.3 Sample size:

The primary statistical analyses will compare the change in epidermal thickness from baseline to 28 days between treatments: betamethasone valerate cream vs crisaborole, utilising the within participant comparisons of left vs right forearm. Assuming that the change from baseline at day 28 in the betamethasone valerate group will be approximately $-4.44\mu\text{m}$ and a standard deviation of $5\mu\text{m}$ (for the change from baseline within each participant), to detect a reduction in this change of 80% to $-0.88\mu\text{m}$ in the crisaborole arm with 80% power, a parallel group study (one group for betamethasone valerate and one group for crisaborole) would require 33 participants in each group.

The study described here is comparing within participants (left vs right arm) rather than a parallel group (between participants) design, however it is assumed that this within patient comparison will have greater power than the parallel group design. This assumption is necessary because no information is available in the literature as to the standard deviation of the difference between change from baseline on the TCS arm and change from baseline on the crisaborole arm. Assuming that the correlation between these two 'change from baseline' measures will be greater than zero then the within participant comparisons can be assumed to have greater power than a parallel group design.

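### Treatment is randomised to left or right forearm because position may matter, but no planned model names side, so any side effect on the change stays in the error of the paired contrast

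*SAP*

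**What the plan says.** Protocol 7.5.1 states: "Allocation of the treatments to the test sites (right/left forearm) will be randomised (to avoid site position-dependent artefacts) 1:1". Protocol 8.7 repeats the reason: "Randomized site allocation to avoid site dependent effects". SAP 2.2 confirms that every participant tests both products, "one on each of the left or right lower volar forearm". Neither document says whether the list is blocked.

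The analyses do not carry side forward:

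- **Primary (SAP 7.1).** The mixed model for change in epidermal thickness has "treatment, timepoint as factors together with a treatment by timepoint interaction, subject as a random effect and baseline as a covariate".
- **Repeated-measures secondary endpoints (SAP 7.2).** "The analysis of three of the secondary endpoints will use a repeated measures mixed model with change from day 1", with the same terms.
- **TEWLts20 (SAP 7.2).** An ANCOVA with "treatment as a factor, subject as a random effect and baseline as a covariate".
- **NMF (SAP 7.2).** A paired test, or an ANCOVA if covariates prove necessary. No covariate is named.
- **Protocol 10.4.2 and 10.4.3.** Paired analyses, again without side.

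The SAP does plan blind-review tables split by arm location, for example "Summary of epidermal thickness change by location" (SAP 9, table BDR1.2). SAP 2.4 allows analysis decisions at blind review. No rule links those tables to a side term.

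**The concern.** Side is the one factor that the trial randomises. It plays the part that period plays in a crossover trial, and it is usual to analyse by it. If the two forearms change differently for reasons unrelated to the product, that difference adds to the spread of the within-person contrast when side is left out.

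The design leaves some room for such a difference. Product is self-applied, dosing is by fingertip unit, and Protocol 8.12 accepts 28 to 112 g of each product as compliant. Handedness is not among the background data listed in Protocol 7.3, so side is the available proxy.

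At stake are some precision in the primary interval, a conditional shift if the sides fall unevenly, and prespecification. Without a stated rule, a side term could be added only after someone has looked at the tables by location.

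**Working it through.** **Inputs from the documents** (Protocol 10.1 and SAP 2.3, 7.5): target difference 3.55 µm, SD of change 5 µm, 33 participants, two-sided 5%.

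**Assumptions, because the documents give neither value:** between-arm correlation r of 0, 0.5 or 0.7, and side effect s (right minus left difference in change) of 0, 1 or 2 µm.

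**The plan's own figure.** A two-sample t-test with difference 3.55 and SD 5 has 79.8% power at 32 per group and 81.1% at 33. The stated 33 is reproduced. It does not depend on side, so the sample size needs no correction.

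**Paired model.** For participant i, D = τ + a·s + e, where a is +1 or −1 according to the side given crisaborole and SD(e) = 5√(2(1−r)). This single day-29 contrast approximates the planned mixed model.

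- Side omitted: Var(D) = 50(1−r) + s², 32 df.
- Side included: residual variance 50(1−r), 31 df, taken here at a 17:16 split.

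The variance added at s = 1 µm is 1/50 = 2% (r = 0) or 1/25 = 4% (r = 0.5). At 2 µm it is 4/50 = 8% or 4/25 = 16%.

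Noncentral-t power at n = 33:

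| r | s (µm) | Side omitted | Side included |
|---|---|---|---|
| 0 | 0 | 79.9% | 79.7% |
| 0 | 1 | 79.1% | 79.7% |
| 0 | 2 | 76.8% | 79.7% |
| 0.5 | 0 | 97.7% | 97.7% |
| 0.5 | 1 | 97.2% | 97.7% |
| 0.5 | 2 | 95.7% | 97.7% |
| 0.7 | 2 | 99.5% | 99.9% |

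If side has no effect, including it costs about 0.1 power point.

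**Chance imbalance.** If allocation is unrestricted, Binomial(33, 0.5) gives a 29.6% chance of a 20:13 split or worse. A 20:13 split shifts the unadjusted estimate by (20−13)/33 = 0.21 × s. That is 0.21 µm at s = 1 µm and 0.42 µm at s = 2 µm, against a target of 3.55 µm. At 17:16 the shift is 1/33 = 0.03 × s.

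**Interval width.** Let d be the imbalance fraction.

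- Half-width with side omitted: t(32) × √{[50(1−r) + s²(1−d²)·33/32]/33}.
- Half-width with side included: t(31) × √{50(1−r)/[33(1−d²)]}.

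At 20:13, d = 7/33 and 1−d² = 0.955. Results at 20:13 are:

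- s = 0, r = 0: 2.507 µm omitted, 2.569 µm included (2.5% wider).
- s = 1 µm, r = 0: 2.532 omitted, 2.569 included.
- s = 1 µm, r = 0.5: 1.808 omitted, 1.817 included (1.8075 and 1.8165 before rounding).

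Setting the two half-widths equal gives the side effect above which adjustment narrows the interval. It is about 0.3 to 0.4 µm at 17:16 and 1.1 to 1.6 µm at 20:13. Averaged over unrestricted allocation it is about 0.9 to 1.3 µm (r = 0.5 to r = 0 in each case).

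**Validity.** In simulated trials (6,000 per setting, r = 0.5, unrestricted 1:1), type I error without side was 4.6% to 5.1%. The mean estimate was 3.54 to 3.56 µm for a true 3.55 µm. With a 3 µm left-right difference in level only, power was 98.0% with or without side.

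**The case against.** The strongest reply is that nothing here is an error. Randomising side makes the treatment estimate unbiased and the test valid whether or not side is modelled, and chance imbalance is sampling variation that the interval already covers. That stands. A reader might infer from the omission that the primary estimate is biased. The documents do not support that, and the simulation shows no bias.

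Second, the primary outcome is change from each arm's own day 1, with baseline as covariate, so a constant left-right difference in level largely cancels. That also stands for endpoints with a day-1 value. It does not help NMF or TEWLts20. Protocol 4.5 and 7.7.10 place tape-stripping on day 29 only, so neither has a day-1 counterpart, although SAP 7.2 words the TEWLts20 model as a change from day 1.

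Third, a 2 µm side effect on change is 56% of the target effect (2/3.55), and nothing in the documents makes it likely. Supervised applications, tube weighing and retraining work against uneven dosing. This is fair, and it is why the cost is shown as a range.

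Fourth, a reader might infer that a side term always tightens the interval. It does not: at 20:13 with a 1 µm side effect the interval is slightly wider.

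Fifth, the tables by location and the blind review offer a route to adding side, and the NMF analysis already permits covariates. The route exists, but no rule says when it would be used.

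**Conclusion.** The point holds as a minor one about efficiency and prespecification. The factor that the trial randomises is absent from the primary model, the secondary mixed models and the TEWLts20 ANCOVA, and it is unnamed for NMF. The loss depends on a side effect on change that the documents do not quantify. It is under 1 power point at an assumed 1 µm. At 2 µm it is 2 to 3 points for correlations of 0 to 0.5, and about 0.4 point at 0.7. The gain in precision from adding side is conditional: it needs a side effect of roughly 1 µm or more unless the split is near even. The imbalance argument also depends on the list being unblocked, which is not stated. The case is clearest for NMF and TEWLts20, where a difference in level has nothing to cancel it. The planned primary analysis remains valid without the change.

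**What to change.** In SAP 7.1 and 7.2, add side (left or right) as a fixed effect, with side by timepoint in the repeated-measures models. For NMF and TEWLts20, regress the within-person treatment difference on side allocation coded +1 and −1, so that the intercept is the treatment effect. State this before the tables by location are reviewed. State also whether the randomisation list is blocked.

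The data are already recorded by arm, so no new collection is needed. The cost is one degree of freedom, or a few with the timepoint interaction. If side has no effect and the split is as uneven as 20:13, the interval is about 2.5% wider.
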